1.2 Objectives

1. Primary Objective:
 - Collection of Treatment Discomfort/Pain Evaluation
2. Additional Objectives:
 - Evaluation of tissue response through Biopsies at multiple timepoints up to 30 days post treatment (optional):
 - Sample staining as appropriate, such as H&E
 - Nano-string for Gene Expression
 - Device comparison treatment with similar low-intensity shockwave device (optional).
 - Photographic evaluation with Vivosight imaging at the 30 and/or 90 day follow up compared to baseline (optional).
 - Photographic evaluation with 2D and/or 3D imaging at the 30 and/or 90 day follow up compared to baseline (optional).
 - Subject treatment assessment through questionnaires (optional):
 - Subject treatment experience questionnaire
 - Subject follow up questionnaire
 - Subject satisfaction questionnaire
 - Clinician treatment assessment through questionnaires (optional):
 - Clinician treatment questionnaire
 - Clinician satisfaction questionnaire
3. Safety Objectives:
 - Collection of Adverse Events

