2.0 PROTOCOL

2.1 Protocol Methodology and Analysis

Methodology:

Subjects are to be enrolled in this clinical study if they are a healthy male or female 18 – 65 years of age. Up to 50 subjects will be enrolled at 2 study centers. Subjects will attend a screening/pretreatment visit which may be performed on the same day as the treatment visit. Subjects may receive up to 5 treatments with the study device. Subjects may also receive treatment

with a similar shockwave device. Subjects may be consented to have biopsies collected at a specific time after their final treatment, which will occur up to 30 days post treatment. Follow up visits may occur 30 and 90 days post last treatment visit. An unscheduled visit or phone call may be performed at any time during the study at the request of the subject or as deemed necessary by the site Investigator.

Analysis:

Upcoming generations are proving to have an interest in non-ablative aesthetic treatments and will drive demand for innovated products, procedures, and practice design.¹ Due to this shift in patient base, practices need to evolve to adapt to the newer generational ideologies. This device will be using the SoftWave device to collect additional data and imaging. Although this device is cleared for use by the U.S. Food and Drug Administration, there is a need to collect additional data, images, and tissue response to expand marketing claims.

Relevance:

There is an increasing demand for new methods and additional cleared indications for non-invasive treatments using shockwave therapy. Another device currently on the market cleared for use is, but are not limited to, the dermaPACE® System.

Testability:

The SoftWave device, had been previously cleared for the activation of connective tissue (FDA 510(k) K182682), the treatment of chronic, full thickness diabetic foot ulcers (FDA 510(k) K191961), and the treatment of superficial partial thickness second degree burns in adults (FDA 510(k) K200926). This study will utilize the collection of data and imaging to support additional marketing claims.

Compatibility:

Although shock wave technology is a well-known and widely use technique for non-invasive treatments, there is still a need to collect additional data and images, and expand marketing claims and device use.

Predictive power:

Assuming there is an acceptable side effect profile, it would be appropriate to expect results for other marketable indications.

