2.2 Protocol Study Design

This is a prospective, open label, multi-center clinical study to collect additional data and imaging for the SoftWave device.

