2.3 Subject Selection Criteria

Subjects will meet the criteria described below:

Inclusion Criteria:

- A healthy male or female 18 – 65 years of age.
- Willing to undergo treatments with the SoftWave device.

- Understands and accepts obligation not to receive any other procedures on the treatment area through the length of the study.
- Understands and accepts the obligation and is logically able to be present for all visits.
- Is willing to comply with all requirements of the study and sign the informed consent document.

Exclusion Criteria:

- Is pregnant or of childbearing potential and not using medically effective birth control, or has been pregnant in the last 3 months, currently breast feeding or planning a pregnancy during the study.
- The subject has a pacemaker or implantable defibrillator.
- The subject has a severe coagulation disorder.
- The subject has open epiphyseal plates.
- The subject has recently had a steroid injection.
- The subject is currently enrolled in an investigational drug or device trial, or has received an investigational drug or been treated with an investigational device within in the area to be treated 6 months to entering this study.
- The subject has any condition or is in a situation which, in the Investigator's opinion, may put the subject at significant risk, may confound study results or may interfere significantly with the subject's participation.

Be sure to list all concomitant medications taken or procedures performed before, during and after the trial.

Subjects will be recruited for the study through the existing patient database and may use advertisements.

Subject populations will not be eligible to participate in the study if they are vulnerable populations such as children, pregnant women, prisoners, institutionalized individuals, and any persons requiring a legally authorized representative as part of the consenting process.

Subject population characteristics that will not be eligible to participate in the study include non-English speaking individuals and people who cannot read or comprehend English. Employees of the Investigator will be participating in the study.

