2.15.4 Analysis of Demographic and Medical History Variables

Summaries will be prepared for all important demographic and medical history variables. For quantitative variables summaries will include the sample size, mean, median, standard deviation, minimum, and maximum. For these variables the treatment groups will be compared using either a t-test or a Wilcoxon Rank Sum test, as appropriate. For categorical variables the summaries will include the sample size and the number and percent of patients for each outcome. For these variables the treatment groups will be compared using Fisher's Exact test. Statistical significance will be declared if the two-sided p-value is < 0.05.

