2.15.6 Analysis of Safety Variables

Safety will be assessed through the degree of pain/discomfort related to the procedure (universal pain scale) and the collection of Adverse Events throughout the course of the study. For each treatment group these variables will be summarized. The summaries will include the number and percent of patients for each outcome. No statistical comparisons will be performed for any of these variables.

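### The optional device comparison gets no between-device difference with its uncertainty, and the only planned between-group tests are independent-sample tests on baseline variables that can count the same subject in both groups

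*Combined protocol and SAP*

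**What the plan says.** Section 1.2 includes among the additional objectives "Device comparison treatment with similar low-intensity shockwave device (optional"). The primary objective in the same section is "Collection of Treatment Discomfort/Pain Evaluation".

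On who gets the second device, section 2.1 says "Subjects may also receive treatment" and continues "with a similar shockwave device". Section 2.3 requires every subject to be "Willing to undergo treatments with the SoftWave device". The design statement in 2.2 reads "This is a prospective, open label, multi-center clinical study to collect additional data and imaging for the SoftWave device"; it describes no allocation. Section 2.15.3 nevertheless defines its analysis sets by reference to randomized patients, and says that data will be analysed by device and overall.

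For demographic and medical history variables, 2.15.4 says "For these variables the treatment groups will be compared using either a t-test or a Wilcoxon Rank Sum test, as appropriate", with Fisher's exact test for categorical variables and significance at a two-sided p < 0.05. For pain and adverse events, 2.15.6 plans number-and-percent summaries by treatment group and then states "No statistical comparisons will be performed for any of these variables". Section 2.15.3 mentions efficacy variables, but no section gives a method for them.

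**The concern.** Formal comparison is planned for baseline characteristics, about which the trial asks no question. It is ruled out for pain and adverse events, where a device comparison would be of interest. A reader of the results would see two columns of percentages and would have to judge the difference by eye. That matters because section 1.1 says the data are meant to support additional marketing claims.

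The baseline tests also assume two separate sets of people. If the comparison device is given to subjects who also receive SoftWave, the groups share members. The tests then tend to show agreement because people are compared with themselves, and a non-significant result could be mistaken for evidence that the groups are balanced.

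**Working it through.** **The plan's own figure.** The only related number is the total of 50 subjects in 2.15.2. No effect size, standard deviation, power or split by device is given, so it cannot be reproduced, and nothing below shows it to be wrong.

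**What is specified for each type of variable.**

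| Variables | Summary by group | Between-group test | Difference with interval |
|---|---|---|---|
| Demographics, medical history (2.15.4) | yes | t-test or rank sum; Fisher | none |
| Pain, adverse events (2.15.6) | yes, number and percent | ruled out | none |
| Satisfaction, photographs, biopsies | per-device analysis promised (2.15.3), no method | none stated | none |

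**Can the groups overlap?** Section 2.1 makes the second device an addition, 2.3 requires willingness to have SoftWave, and no comparator-only group or allocation rule appears. Overlap is therefore possible. Its extent is not stated.

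**Effect of overlap on a baseline t-test.** Let n1 subjects be in the SoftWave group, n2 in the comparator group and m in both. The pooled-variance test assumes that the difference in means has variance SD² × (1/n1 + 1/n2). The true variance is SD² × (1/n1 + 1/n2 − 2m/(n1 × n2)). Take n1 = 50 (from 2.15.2) and assume that all comparator subjects also receive SoftWave, so n2 = m.

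- m = 25: assumed 0.02 + 0.04 = 0.06; true 0.06 − 50/1250 = 0.02. The assumed standard error is √3 = 1.732 times too large. The critical value (73 df) of 1.993 acts as 1.993 × 1.732 = 3.45, so the rejection rate is about 0.06%.
- m = 10: assumed 0.02 + 0.10 = 0.12; true 0.12 − 20/500 = 0.08. The ratio is √1.5 = 1.225. The critical value (58 df) of 2.002 acts as 2.002 × 1.225 = 2.45, so the rejection rate is about 1.4%.
- m = 50: true variance 0.04 − 100/2500 = 0. The groups are the same people; the difference is zero and Fisher's p is 1.

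Simulation of the first two cases agrees closely (about 0.05% and 1.4%). With no overlap the rate is the nominal 5%. The rank sum and Fisher tests rest on the same independence assumption.

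**What a paired contrast could deliver.** The half-width of a 95% interval for the mean within-subject pain difference is t(n−1) × SD × √(2(1 − ρ)/n). The documents give no SD, correlation ρ or number treated with both devices. Assume n = 20, so t(19) = 2.093:

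- SD 2, ρ 0.5: 2.093 × 2 × √(1.0/20) = 0.94 points.
- SD 1.5, ρ 0.7: 2.093 × 1.5 × √(0.6/20) = 0.54 points.
- SD 3, ρ 0.3: 2.093 × 3 × √(1.4/20) = 1.66 points.

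**The case against.** The comparison is optional, is listed only among the additional objectives, has no success criterion in 2.15.1, and was added by amendment (Appendix A). Side-by-side description without inference is a defensible choice for a non-randomised component. The sentence in 2.15.6 may mean only that no hypothesis tests will be run. Much of this stands: descriptive reporting would be acceptable if the plan said that this is what the objective amounts to. It does not. It calls the objective a comparison, refers to randomized patients, and tests baseline variables for significance. Even if 2.15.6 excludes only tests, no difference with an interval is specified anywhere.

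Three stronger readings are tempting, and the documents do not support them:

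- A reader might infer that the device comparison yields no estimates at all. Sections 2.15.3 and 2.15.6 plan per-device analysis and per-group summaries; what is missing is the difference between devices and its uncertainty.
- A reader might infer that all outcome comparisons are forbidden. The exclusion covers pain and adverse events only. For satisfaction, photographs and biopsies the plan is silent. The jump in numbering from 2.15.4 to 2.15.6 is weak evidence by itself, since two sections are also numbered 2.13.
- A reader might infer that subjects will be compared with themselves. Section 2.1 makes that possible, not certain.

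**Conclusion.** The point holds in this form. No between-device difference with uncertainty is specified for any outcome, and for pain and adverse events statistical comparison is ruled out. The only planned between-group tests answer no trial question and become invalid wherever a subject is in both groups.

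The size of the invalidity depends on the overlap, which the documents leave open: about 0.06% rejection in place of 5% with 25 of 50 shared, about 1.4% with 10 of 50 shared, and no usable test with all shared. If the groups turn out to be disjoint, the tests keep their nominal level but still serve no stated question.

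A paired estimate appears feasible within the planned total. With 20 subjects on both devices the half-width would be 0.54 to 1.66 points on the 0 to 10 scale, for an assumed SD of 1.5 to 3 and correlation of 0.3 to 0.7. This illustrates precision and is not a forecast.

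**What to change.** 1. **Section 2.1:** state whether the device comparison is within-subject or between-subject. Reconcile the reference to randomized patients in 2.15.3 with the design.
2. **Section 2.15.4:** delete the between-group tests and p-values. Describe subjects overall and by device received.
3. **Section 2.15.6:** replace the sentence excluding comparisons with: *No hypothesis tests will be performed. For subjects who receive both devices, the within-subject SoftWave minus comparison-device difference in pain score (each subject's mean over that device's treatments) is reported as a mean with 95% CI, and the proportion of subjects with an adverse event at the area treated with each device as a paired difference with 95% CI where events can be attributed to one device. For subjects who receive one device only, differences are reported with 95% CI and labelled non-randomised.*

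The text names each subject's mean score because up to five treatments are allowed and pain is scored at treatment visits (2.7 and the visit schedule). The limit on attribution is needed because section 14.0 defines its relationship ratings for SoftWave treatments only.

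The cost is plan wording and a few lines of analysis. The downside for the sponsor is that an imprecise or unfavourable device difference becomes visible. If the sponsor prefers description only, 1.2 and 2.15.6 should say so; the baseline tests should still go.

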3.0 RISK ANALYSIS AND MANAGEMENT

3.1 Risk Determination

This device study used in this study does not meet the FDA definition for a Significant Risk Device study per 21 CFR 812.3(m). Therefore, the sponsor determines that this is a non-significant risk device study.

Significant risk device means an investigational device that:

- (1) Is intended as an implant and presents a potential for serious risk to the health, safety, or welfare of a subject;
- (2) Is purported or represented to be for a use in supporting or sustaining human life and presents a potential for serious risk to the health, safety, or welfare of a subject;
- (3) Is for a use of substantial importance in diagnosing, curing, mitigating, or treating disease, or otherwise preventing impairment of human health and presents a potential for serious risk to the health, safety, or welfare of a subject; or
- (4) Otherwise presents a potential for serious risk to the health, safety, or welfare of a subject.

3.2 Risk Management

The Investigator in this clinical trial has been invited to participate based on his/her previous experience with the use of the system and/or similar systems and industry experience. Experience with treatments is the most critical element in managing subject risk in this trial.

In addition, as with any study, there is a risk of bias. Objective evaluation methods may be used in conjunction with subjective evaluation methods when feasible. The value of the compensation to the clinical investigator for conducting the study is not influenced by the study outcome. If photographic results are listed as the primary objective, they are to be evaluated by blinded evaluators who did not partake in the study. If information concerning investigator assessment of improvement or investigator satisfaction is collected, then it is not listed as an objective for the study.

All other known risks will be disclosed to the subject via the informed consent process. Since this is an elective procedure and the subjects are volunteers, it can be assumed that their signature on the informed consent is indicative of their agreement to accept the risks involved.

The risks to the subjects who participate in this study are the same as those for the subject undergoing similar non-ablative shockwave treatment. It is possible to have an adverse reaction to the SoftWave device. There may be some side effects that we don't know about yet.

3.3 Risk Analysis

CONTEXT OF THE PROPOSED INVESTIGATION:

Shockwave is an effective approach to healing the human body using acoustic waves to stimulate the body's natural processes for self-repair. This technology is not new and although it has been in the marketplace for over 14 years in Europe, it just recently received FDA clearance in the US.

Shockwaves are created through the use of an electrode contained within a soft latex dome filled with water. When charged with electricity, the electrode creates a spark under the water. This spark creates a hot bubble of gas that expands into the surrounding water and produces the shockwave that travels out of the applicator and into the affected area being treated. These high energy acoustic waves penetrate deep into damaged tissue causing cellular walls to become permeable allowing exosomes to escape into the interstitial tissue mimicking cellular injury which triggers the migration of your body's own stem cells to the area for sustained long-term healing.

ASSESSMENT OF RISKS OF THE PROPOSED INVESTIGATION:

The risk identified with the overall clinical investigation is the integrity of the data collected. There are multiple clinical mitigation strategies for the risk identified. Proper training on the protocol will be performed. Monitoring of the study will be implemented to minimize subject and data risks.

ASSESSMENT OF BENEFITS OF THE PROPOSED INVESTIGATION:

The subject may or may not have improvement for the indication treated.

CONSIDERATION OF PATIENT PREFERENCE INFORMATION:

Many physicians support the use of shockwave devices for non-invasive treatments due to current patient satisfaction with their results with the currently available devices. However, there is still a level of interest in expanding indications and marketing claims for shockwave devices.

ASSESSMENT OF UNCERTAINTY:

There is uncertainty of efficacy results for expanding marketing claims while using the SoftWave device in this study.

CONCLUSION:

This study is determined to be a non-significant risk study and the risks posed to the subjects and integrity of data are acceptable.

Patient population to be enrolled in this clinical study:

Total anticipated population: 50 Subjects

Age Range: 18 – 65 years of age

Gender: Male or Female

Condition: Conditions that may be treated with the activation of connective tissue.

4.0 DEVICE DESCRIPTION AND SPECIFICATIONS

The SoftWave device used in this study is cleared for use by the U.S. Food and Drug Administration (the FDA) for the following indications:

K200926:

The OrthoGold 100 is indicated to provide acoustic pressure shockwaves in the treatment of superficial partial thickness second degree burns in adults (22 years and older). The OrthoGold 100 is indicated for use in conjunction with standard of care burn treatment(s).

K191961:

The OrthoGold 100™ is indicated to provide acoustic pressure shockwaves in the treatment of chronic, full-thickness diabetic foot ulcers with wound areas measuring no larger than 16 cm², which extend through the epidermis, dermis, tendon, or capsule, but without bone exposure. The OrthoGold 100 is indicated for adult (22 years and older), diabetic patients presenting with diabetic foot ulcers greater than 30 days in duration and is indicated for use in conjunction with standard diabetic ulcer care

K182682:

The OrthoGold 100 is intended for the activation of connective tissue.

The device used in this study is considered investigational because it may not be used in accordance with the currently cleared instructions for use and may use the data collected for additional marketing claims and indication.

SoftWave Technical Data:

Water System	
 • Closed system • Content of the water cartridge: 450 ml Water (15.22 fl oz) • Adjustable water flow • Fill time of the reflector: Approx. 25 seconds
Shock wave generator	
 • The coupling to the treatment

	
area happens via water membrane.
 
 • Principle: electro hydraulic, spark gap under water caused by discharge of high voltage condensers. • Shock wave release frequency: 0.5 to 8 Hz.
Operation- and display elements	
 • Operation monitor and touch wheel at the front side of the device • Power on / off, displayed by control lamp in switch • Footswitch to release shock waves
Supply	
 • Voltage supply: AC 100- 240 V, ± 10 %, 50/60 Hz • Single phase • Class I equipment • Type B • Power consumption: 100V/200VA 240V/200VA

Changes to the SoftWave device are not anticipated during the investigation.

The comparison device that may be used is called the Eclipse Evive shockwave device. This is an FDA Class 1 device that falls under FDA code Sec. 890.5660 for marketing. You can find additional information on the device's website here: <https://www.eclipsemed.com/evive/>.

5.0 MONITORING PROCEDURES

The Sponsor Standard Operating Procedure (SOP) for monitoring the investigative site will be followed. The sponsor will train the site following sponsor SOP's and may be present at initiation of treatment. The sponsor will also monitor the site periodically. The Investigator/Institution will permit trial-related monitoring, audits, IRB/IEC review, and regulatory inspections by providing direct access to source documents. The sponsor may request intermediate data following each visit to evaluate treatment progress. Case Report Forms will be reviewed for current data and Regulatory Binders will also be reviewed for correct documents. The sponsor will collect data at the end of the follow up period. The sponsor will list the study on clinicaltrials.gov when required by FDA regulations.

The monitoring plan for this study is outlined in the Cynosure Monitoring Plan.

ASSIGNED CLINICAL RESEARCH MONITOR:

Monitor #1

Name: [name]

Institution: Cynosure, LLC

Address: [name]

